## **1. Introduction**

Mountain biking has developed into a popular sport performed by both amateurs and professionals. Physical activity is often related to an increasing risk of injury which may lead to high socioeconomic costs. To avoid accident-related injuries, each racing discipline demands its own set of specific skills and training regimens. The aim of this study is to perform a descriptive analysis of the causes and effects of mountain biking related injuries in amateur and professional athletes.

## **2. Methods**

A survey (as outlined below) of mountain biking related injuries will be conducted on the participants of the Swiss Epic mountain bike event in 2017 held in Valais. The retrospective questionnaire is designed in accordance with existing literature ((Gaulrapp et al., 2001; Lareau and McGinnis, 2011), will include 25 questions and will be translated into English, French, Italian, Spanish and German. The participants will be asked to tick the most appropriate answer. The questionnaire aims to assess the athletes' 1) basic demographics, riding level and years of experience, 2) number of races per year and mean hours of training per week, 3) number and kind of suffered injuries related to mountain biking and medical treatment requirement, 4) and amount and kind of protective gear items.

## **3. Statistical analysis plan**

Data analyses will be performed using the Statistical Package for Social Sciences (SPSS), version 24.0 (IBM Corporation, Armonk, NY, USA).

Descriptive statistics [means  $\pm$  standard deviations (SD) and relative frequencies (%)] will be retrieved. Pearson correlations will be used to assess correlations between the outcome variables. Chi-squared tests will be applied to determine group differences of injury prevalence and the occurrence of severe, respectively mild injury events. Multivariate logistic regressions will be performed to evaluate predictive factors among the outcome variables (independent variables) of severe injury events (dependent variable; no severe injury = 0 versus severe injury = 1) in elites and amateurs separately. Independent samples t-tests will be used to evaluate mean group differences in demographics, and training and injury related variables between the elite and the amateur mountain bikers. P-values  $< 0.05$  will be considered as statistically significant. According to Cohen (1992), effect sizes will be calculated for the correlation analyses and defined as follows;  $r = 0.20$  small,  $r = 0.50$  medium,  $r = 0.80$  strong.

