**2. On what level do you participate in mountain biking?**

recreational       amateur       elite-amateur       professional

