**9. Number of injuries obtained during mountain biking**

\_\_\_\_\_

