**10. How long ago was your most recent injury?**

\_\_\_\_\_ /months

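### The elite–amateur comparisons are not adjusted for riding exposure, so they describe cumulative injury burden and cannot show a difference in risk per amount of riding

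*Combined protocol and SAP*

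**What the plan says.** Section 1 sets a descriptive aim, to "perform a descriptive analysis of the causes and effects of mountain biking related injuries" in amateur and professional athletes. Section 2 lists among the questionnaire's targets years of experience and the "number of races per year and mean hours of training per week".

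Section 3 plans these analyses that bear on the two groups:

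- "Chi-squared tests will be applied to determine group differences of injury prevalence and the occurrence of severe, respectively mild injury events".
- "Independent samples t-tests will be used to evaluate mean group differences in demographics, and training and injury related variables" between elite and amateur riders.
- Multivariable logistic regression for severe injury, fitted "in elites and amateurs separately".
- Pearson correlations among the outcome variables.

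The significance threshold is p < 0.05.

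In the questionnaire, exposure is covered by item 1 (years), item 6 (estimated weekly training hours for each season) and item 7 (races per year). Item 9 asks for the "Number of injuries obtained during mountain biking" and sets no recall window. Item 12 grades only the worst injury. Item 10 asks "How long ago was your most recent injury", in months. Rider level comes from item 2, "On what level do you participate in mountain biking", which has four answer levels. Section 3 refers to two groups and does not say how the four levels are combined.

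**The concern.** Both the number of injuries and the severity of the worst one build up with riding. If one group rides more hours or has ridden for more years, it will tend to show more injuries and more severe worst injuries even when an hour of riding is equally dangerous for both. Conversely, a real difference in hourly risk can be cancelled by a difference in exposure. The planned between-group tests have no denominator, offset, stratum or covariate, and a model fitted within each group gives no contrast between groups. The study would therefore hold the data needed to separate riding more from being injured more per amount of riding, but would have no planned analysis that does so. Any adjustment added later would be chosen after the data had been seen.

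**Working it through.** **Two inferences.** The chi-squared sentence names no groups; elite versus amateur is taken because it is the only grouping in section 3. The item 9 count is taken to be one of the injury variables in the t-tests, although that phrase could also mean days to return to sport or work (items 15 and 16).

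**Inputs.** The documents give no sample size, injury rate or hours by group, so there is no figure to reproduce. Every number below rests on assumptions.

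**1. Closed form, equal hourly risk.** Let μ be the mean number of injuries per amateur and k the elite/amateur exposure ratio, with Poisson injuries.

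- P(ever injured) = 1 − exp(−μk).
- μ = 0.5: amateurs 1 − exp(−0.5) = 39%; elites at k = 2, 1 − exp(−1) = 63%.
- μ = 1: 63% against 1 − exp(−2) = 86%.
- With 100 riders per group and two-sided 0.05, the chance of a significant result is Φ[(d − 1.96·SE₀)/SE₁], where d is the difference in proportions and SE₀ and SE₁ are its pooled and unpooled standard errors. For μ = 0.5 this is Φ[(0.239 − 1.96 × 0.0707)/0.0686] = 0.93; for μ = 1 it is 0.97.
- Over μ from 0.25 to 2 and k from 1.5 to 3 the range is 0.31 to above 0.99.

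Severity moves too. If each injury is severe with probability q, then P(worst is severe, given injured) = [1 − exp(−μkq)]/[1 − exp(−μk)]. With q = 0.2 and μ = 1 this is 29% at k = 1, 38% at k = 2 and 48% at k = 3.

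Masking: half the hourly risk with twice the exposure leaves μk unchanged (0.5 × 2 = 1), so prevalence is 63% in both groups.

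**2. Simulation with variation between riders.** Assumed: 60 elites and 240 amateurs; 0.25 injuries per 1000 h; 15% of injuries severe; lognormal hours and years (CV 50%); gamma frailty (variance 0.5). The exposure ratios are 0.70 (7 v 10 h/week, 8 years each), 1.0, 1.43 (10 v 7 h/week, 8 years each) and 3.1 (15 × 10 = 150 v 6 × 8 = 48). Crude rejection under equal hourly risk, 1,000 replicates:

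| Elite exposure | Prevalence | Count t-test | Any severe, all riders | Severe, injured riders |
|---|---|---|---|---|
| 0.70 | 23% | 28% | 8% | 5% |
| 1.0 | about 4% | about 4% | about 4% | about 4% |
| 1.43 | 25% | 39% | 13% | 5% |
| 3.1 | 98% | 100% | 81% | 28% |

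Prevalence is 42% v 51% at 0.70 and 51% v 42% at 1.43 (elites first), so the sign follows the unknown gap. At 1.43 with a 30% lower elite hourly rate (1.43 × 0.7 = 1.00), prevalence is 42% in both groups. The last two columns also show that the severity denominator matters.

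**3. Would a pooled count model help?** A negative binomial model with group, log years and log hours, under the same assumptions:

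- Hours reported without random error, equal risk: rate ratio 0.99–1.01, rejection 4–6%.
- 30% lower elite rate: power 30–38%, typical 95% CI about 0.44–1.1. At 1.43-fold, power is 24% with 30/270 riders and 49% with 150/150. With 60/240 riders it is about 21% at 0.1 injuries per 1000 h and 81% at 2 per 1000 h.
- Random error in hours, the same in both groups, true ratio 1, at 0.70/1.43/3.1-fold: rate ratio 0.90/1.09/1.32 (error CV 30%) and 0.83/1.17/1.60 (CV 50%, rejecting 11/14/62%). The coefficient for hours is attenuated, so part of the exposure gap stays in the group term. The same data with log exposure as offset give 0.98–1.07 and reject 4–6%.
- Elites' current hours overstating their career hours by 25%: the covariate form gives 0.81–0.84 and rejects 11–17%; the offset form rejects 15–24% (expected ratio 1/1.25 = 0.80).
- Racing itself adding risk (0.01 injuries per race, 15 v 5 races a year): rate ratio 1.64–1.70 without races and 1.00–1.05 with them.

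Neither form is safe against every error, so both should be shown.

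**The case against.** The strongest reply is that nothing here is an error. The aim is descriptive, section 3 speaks of prevalence, and no section promises a rate per hour. That stands. A reader might infer that the crude tests are invalid or have an inflated false-positive rate. The documents do not support this: a rejection caused by unequal exposure is correct for cumulative burden and misleads only if taken as risk.

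A reader might also infer that exposure is ignored altogether. It is not. Training variables are compared between the groups, so a gap would be visible beside the injury result, and they may enter the correlations and the within-group models. None of this adjusts the group contrast.

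A third reply concerns the remedy. Item 6 records estimated current training hours, not career riding, and a covariate model can present residual confounding as an adjusted difference. This also stands, and it is why the covariate form should not be the only model. The severe-injury and 12-month logistic models add little: for a 30% lower elite rate their power is 4–7% and 2–8%.

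What the reply does not remove is that section 3 tests group differences for significance and seeks predictors of severe injury, and the questionnaire's introduction speaks of preventing injury. A reader could easily take a significant difference as one of risk, and the plan has no sentence against it.

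**Conclusion.** The point holds as a limit on interpretation and a cheap improvement. No planned analysis adjusts the elite–amateur contrast for exposure, so a crude difference, or its absence, does not show whether risk per amount of riding differs.

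It would go too far to infer that elites will look worse, or by how much. Amateurs could have the greater exposure, and the division of the four item 2 levels into two groups itself sets the gap. The simulated figures show only that moderate gaps can matter. They depend on assumed group sizes, hours and spread, and the crude-test and rate-ratio results use a single assumed rate of 0.25 injuries per 1000 h; only the power of the covariate model was varied over that rate.

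**What to change.** 1. Keep the crude tests and add: *Crude group comparisons describe cumulative injury burden, not risk per amount of riding.* State how the four levels of item 2 form the elite and amateur groups, and whether severe versus mild is counted among all riders or injured riders.

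2. Add one supporting analysis of the item 9 count: a pooled negative binomial (or robust Poisson) model with a group term, reported as a rate ratio with 95% CI in two forms: (a) offset log(years × 52 × mean of the four seasonal hours); (b) log years and log hours as covariates. Show each without and with races per year, because racing may be part of what distinguishes elites and the two versions answer different questions. State a rule for zeros, for example replacing 0 years or 0 h/week by 0.5, reporting how many riders this affects and repeating the fit without them. This rule was not tested, since no zeros arose in the simulation.

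3. State that item 6 is an estimated current proxy for career riding. Error that differs by group biases both forms; random error common to both groups biases form (b) through attenuation; form (a) assumes injuries proportional to hours. Read the CI rather than the p-value, and do not take a non-significant result as equal risk.

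4. Treat the pooled severe-injury logistic model and the 12-month comparison (items 9 and 10) as optional.

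Cost: SAP wording and a few extra model fits, with no new question or data. The downside is an approximate rate ratio of low precision.

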**11. Mechanism of injury**

loss of control       loss of traction       collision with object       collision with rider       mechanical problem  
 unknown       other \_\_\_\_\_

**12. Severity of injury** (if more than one injury occurred, choose the most severe one)

no medical treatment needed     self-administered medical treatment     MD administrated medical treatment     Medical treatment in ER     Overnight hospitalization

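### The separate severe-injury models for elites and amateurs have no limit on predictors: chance 'predictive factors' are likely at any sample size, and a small group's model may not be estimable

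*Combined protocol and SAP*

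**What the plan says.** The statistical analysis plan (section 3) contains one multivariable analysis: "Multivariate logistic regressions will be performed to evaluate predictive factors among the outcome variables (independent variables) of severe injury events". The dependent variable is binary ("no severe injury = 0 versus severe injury = 1"), and the models are run "in elites and amateurs separately". P-values below 0.05 "will be considered as statistically significant".

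The section gives no predictor list, maximum number of predictors, selection method, penalisation, rule for sparse data or multiplicity adjustment.

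Three facts that determine how many severe events each model will have are also absent:

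- **Sample size.** The survey "will be conducted on the participants of the Swiss Epic mountain bike event in 2017 held in Valais", but no expected number of respondents is given.
- **Cut for a severe injury.** Questionnaire item 12 offers five ordered treatment levels and asks for one answer ("if more than one injury occurred, choose the most severe one"). The plan does not say which levels count as severe.
- **Group definition.** Item 2 ("On what level do you participate in mountain biking") offers four levels. The plan does not map them to elite and amateur.

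**The concern.** The candidate pool is large. The questionnaire "will include 25 questions", plus gender, date of birth and race format, and the plan's wording admits nearly all of them as predictors. The sample is then split in two, and each part must support its own model.

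Two separate problems follow. First, many coefficients tested at 0.05 will produce significant results by chance, and the plan would report these as predictive factors. The questionnaire's introduction tells riders that the survey may help safety and prevention, so a spurious risk factor could be acted on. Second, if the smaller group has few severe injuries, or rarely ticked categories, maximum-likelihood estimates can separate (odds ratios run to infinity) or be badly inflated.

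**Working it through.** The plan states no sample size, event count or power, so there is no figure of its own to reproduce.

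**1. Parameters per model, pre-injury items only** (gender, date of birth, race format, items 1 to 8)

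Age 1, gender 1, race format 3, years of riding 1, level within group 1, motivation 6, rider type 4, pedal system 1, mean weekly hours 1, races per year 1, protective gear 5:

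1 + 1 + 3 + 1 + 1 + 6 + 4 + 1 + 1 + 1 + 5 = 25.

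Coding the third gender option and the open gear option adds 2, giving 27. If every item except severity enters, the count is about 70. If only the pre-injury domains named in section 2 enter (age, gender, level, years, races, hours, gear), it is 1 + 1 + 1 + 1 + 1 + 1 + 5 = 11.

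**2. Chance of at least one false predictor**

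The inputs are 0.05 per test (section 3), taken as two-sided, and k independent predictors with no true effect. The formula is 1 - 0.95^k for one model and 1 - 0.95^(2k) for both.

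| k per model | One model | Both models |
|---|---|---|
| 5 | 23% | 40% |
| 11 | 43% | 68% |
| 25 | 72% | 92% |
| 27 | 75% | 94% |

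With 25 parameters, the expected number of false positives over both models is 50 x 0.05 = 2.5.

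The formula does not contain the sample size. Null simulations of 25-parameter models at an assumed 30% severe agree. Among fits that succeeded, at least one P < 0.05 appeared in 65%, 76%, 73%, 71% and 71% at 100, 150, 250, 400 and 800 riders. A second simulation with 27 predictors gave 87% at 100 riders with 20% severe, and 78% at 400 riders with 30% severe. So 72% is an approximation, and very sparse fits can depart from it in either direction.

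**3. Chance that the model cannot be fitted**

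Group size and proportion severe are assumptions here. In the 27-predictor simulation, about half the predictors were continuous and the rest binary with 10% to 50% prevalence. A fit failed if it did not converge or a coefficient diverged.

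| Riders in group | Severe (assumed) | Severe events | Fits failing |
|---|---|---|---|
| 50 | 10% | 5 | 100% |
| 100 | 20% | 20 | 48% |
| 200 | 20% | 40 | 6% |
| 400 | 30% | 120 | 0% |

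Failure also depends heavily on how answers spread over categories. With the 25 questionnaire parameters, 100 riders and 30% severe, about 11% of fits fail with even categories and 70% with moderately skewed ones. Over 20-30% severe, the range at 100 riders is about 10% to 95%. At 400 riders it is 7% or fewer for even to moderately skewed answers. Strong skew is worse: one such setting at 30% severe gave 85% failure at 250 riders, so the 400-rider figure should not be read as covering that case.

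**4. What a short list would need**

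The convention of 10 events per parameter is not in the documents. Under it, five parameters need 5 x 10 = 50 severe events in a group. At an assumed 30%, 20% or 10% severe, that is 50/0.30 = 167, 50/0.20 = 250 or 50/0.10 = 500 riders. Twenty-five parameters would need 25 x 10 = 250 severe events.

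**The case against.** **The models might be fine.** A reader might infer that the models will break down. The documents do not support that. They give no group sizes, no cut for severe injury and no elite/amateur mapping, and plausible assumptions take the failure rate from 100% to 0%. Any single failure percentage is one point in that range. What stands is that the plan has no protection if a group turns out small.

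**More events would solve it.** A reader might also infer that the false predictors come from too few events, so that a larger survey, or about 250 severe injuries per group, would remove them. It would not. The rate stays at roughly 70-75% up to 800 riders, because it comes from the number of tests.

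**Twenty-five is not the plan's number.** This is fair. Section 3 does not say that all items enter together, and it names no estimation or selection method. A reading confined to the domains in section 2 gives about 11 parameters. Even so, the chance of a false predictor is 43% per model and 68% over both, and nothing in the plan holds the analyst to that reading.

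**The aim is descriptive.** The Introduction says so, which softens the consequence. It does not remove it, because section 3 speaks of predictive factors and attaches a significance threshold to them.

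**Conclusion.** The concern holds in a conditional form. As written, the plan allows a model of about 25 parameters in each group, tested at 0.05 without adjustment. With no true predictor, each such model reports at least one about 72% of the time, largely regardless of sample size. That figure rests on the parameter count and on approximate independence of the tests.

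Failure to fit is a possibility, not a prediction. At an assumed 20-30% severe it ranges from about 10% to 95% of fits at 100 riders, and is 7% or fewer at 400 unless answers are strongly skewed. The change is worth making because this is the plan's only multivariable analysis and the remedy is cheap.

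**What to change.** Before the data are seen, amend section 3 as follows:

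- **Predictors.** Name a short pre-injury set for each model, for example age, gender, years of riding, mean weekly hours, and rider type in two classes. State how its size will be scaled to the severe events observed in the smaller group. Ten events per parameter is a usable convention, but it should be labelled as one.
- **Estimation.** Fit with Firth-penalised logistic regression and report odds ratios with 95% CI. This addresses separation, not multiplicity.
- **Interpretation.** Label the results exploratory, or apply an adjustment such as Holm. One of the two is needed because five predictors still give a 23% chance of a false predictor per model and 40% over both.
- **Optional.** If the elite group has too few events, a pooled model with level as a covariate is possible. It gives up elite-specific estimates, so this is a trade-off for the sponsor and not a requirement.

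The cost is SAP wording, plus an SPSS extension or a second package for the Firth fit. No new data are needed. The downside is that fewer items can be screened as predictors.

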## Mountain biking Injury Questionnaire

*Thank you for agreeing to take part in this important questionnaire about mountain biking injuries. The information we can obtain from this survey may help to improve the knowledge about injury prevalence in mountain biking. With this knowledge, it may be possible to improve safety in future and prevent injury.*

*Be assured that all answers you provide will be kept in the strictest confidentiality. This survey is anonymous. Do not write your name on the survey.*

*Please tick only the most correct answer.*

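### Riders who were never injured have no route through items 10 to 17, and the SAP does not say how they are coded, so the zero group of the severe-injury analysis is undefined

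*Combined protocol and SAP*

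**What the plan says.** Section 2 (Methods) surveys the participants of the 2017 event, not only those with an injury. Section 3 (Statistical analysis plan) plans chi-squared tests of "group differences of injury prevalence and the occurrence of severe, respectively mild injury events". It also plans logistic regressions, in elites and amateurs separately, of "severe injury events (dependent variable; no severe injury = 0 versus severe injury = 1"), with predictors described only as "predictive factors among the outcome variables (independent variables"). It does not say which questionnaire item supplies severity, where mild ends and severe begins, which riders are analysed, or how missing answers are handled.

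On the questionnaire, item 9 ("Number of injuries obtained during mountain biking") is an open count, so zero is possible. No skip instruction follows. Items 10 to 17 ask about timing, mechanism, severity, location, type, days to return to sport and to work, and recovery. None offers a not-injured or not-applicable answer. Item 11 has boxes for unknown and other, but neither means no injury. Item 12 grades severity upward from "no medical treatment needed" and advises riders with several injuries, not riders with none. The general instruction is "Please tick only the most correct answer".

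**The concern.** A rider with no injury reaches item 12 and has two options: leave it blank, or tick the lowest box, which is literally true but is also the answer for a real injury that needed no treatment. If the analyst takes severity from item 12 as answered, the two responses lead to different places.

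- **Blank.** The outcome is missing, and a complete-case logistic regression omits the rider. If most never-injured riders do this, the model describes severity among the injured rather than the occurrence of severe injury among riders.
- **Lowest box.** The rider is 0 in the regression but is counted as a mild injury event in the chi-squared test and in the summaries of items 10 to 17.

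The regression can then answer either of two questions, and the plan does not choose between them. Restricting to injured riders conditions on a consequence of the predictors, so a factor that adds only mild injuries can look protective against severe ones. Items 15 and 16 have a similar problem: a never-injured rider who writes 0 days lowers the mean that enters the t-tests, and one who leaves a blank does not.

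**Working it through.** The plan gives no sample size, injury rate or severity rate, so there is no figure of its own to reproduce. All rates below are assumptions. Severity is assumed to come from item 12, which the SAP does not state.

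**Notation.** *u* is the share never injured and *s* is the severe share among the injured. Among injured riders the severe share is *s*; among all riders it is (1 − *u*)*s*. The truly mild share of all riders is (1 − *u*)(1 − *s*), and it appears as *u* + (1 − *u*)(1 − *s*) if every never-injured rider ticks the lowest box. With never-injured riders coded 0, their share of the zero group is *u* / [*u* + (1 − *u*)(1 − *s*)].

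**1. Shares, for *u* from 10% to 50% and *s* from 20% to 40%.**
- The severe share is 20–40% among injured riders and 10–36% among all riders.
- Never-injured riders form 12% (0.10/0.82) to 63% (0.50/0.80) of the zero group.
- At *u* = 30% and *s* = 20%, the mild share is 0.70 × 0.80 = 56%. If all never-injured riders tick the lowest box it appears as 0.30 + 0.56 = 86%.
- At *u* = 30%, mean days to return fall to 0.70 of the injured-rider mean if all never-injured riders write 0.

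**2. A factor that raises mild injury only.** Severe injury is 15% at both factor levels; mild-only injury is 60% with the factor and 30% without.
- All riders: (0.15/0.85) / (0.15/0.85) = 1.0.
- Injured riders only: (0.15/0.60) / (0.15/0.30) = 0.25/0.50 = 0.50.
- Half of the never-injured blank at each level (never injured 25% and 55%): the zero groups are 0.60 + 0.125 = 0.725 and 0.30 + 0.275 = 0.575, so the odds ratio is 0.575/0.725 = 0.79.

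**3. A factor whose direction reverses.** Never injured 10% versus 40%; severe among the injured 25% versus 35%.
- Injured riders only: (0.25/0.75) / (0.35/0.65) = 0.62.
- All riders: risks 0.90 × 0.25 = 0.225 and 0.60 × 0.35 = 0.21, giving (0.225/0.775) / (0.21/0.79) = 1.09.

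**4. Equal severity among the injured (30% at both levels).** The injured-only odds ratio is 1.00.
- Never injured 10% versus 30%: all-rider risks 0.27 and 0.21, odds ratio 1.39.
- Never injured 10% versus 50%: all-rider risks 0.27 and 0.15, odds ratio 2.10.
- Never injured 20% at both levels: risks 0.24 and 0.24, odds ratio 1.00 under either denominator.

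**The case against.** The strongest reply is that the plan can already be read correctly. Item 9 identifies riders with no injury, and a code of 0 for no severe injury, taken literally, includes them. A reader might infer that these riders must be either lost as blanks or counted as mildly injured. The documents do not support that: an analyst could code them 0 from item 9, and nothing in the SAP prescribes listwise deletion. This part of the objection stands. What it leaves is that the SAP does not state the rule, so the result rests on an unwritten choice.

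It is also true that a tick in the lowest box does no harm to the regression. It gives the same 0 that the literal reading gives; the damage is confined to the mild-injury test and the summaries of items 10 to 17. In the regression only unrecoded blanks matter.

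Severity among injured riders is a legitimate question, and the stated aim is descriptive. The injured-only odds ratio is therefore not wrong in itself. It misleads only if reported as the risk of severe injury among riders.

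Finally, item 9 has no time window and so reads as a career count. The never-injured share could be small, and the effect with it. The documents do not settle this.

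**Conclusion.** The point holds as a gap in both the form and the SAP. Never-injured riders belong to the surveyed group, the form gives them no valid answers from item 10 to item 17, and the SAP does not fix their coding, so the zero group and several denominators depend on how riders happened to answer.

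The size is unknown. The contrasts of 0.50 against 1.0 and 0.62 against 1.09 are assumed scenarios in which severity comes from item 12 and every never-injured rider is blank and dropped. A reader might take 0.50 as an estimate of the bias in this survey; it is not one. The distortion is absent when the never-injured share and the severe share among the injured are both equal across factor levels. The plan cannot presume such equality, because it sets out to test differences in injury prevalence and to look for predictors. The analysis can be rescued from item 9 where that item is answered, provided the rule is written before the data are seen.

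**What to change.** **On the form**, after item 9 add: *If 0, please enter 0 and go to question 18.* Item 18 has a no answer, so it need not be skipped.

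**In the SAP:**
- Derive never-injured status from a zero at item 9, overriding any tick at item 12.
- Keep these riders, coded 0, in the all-rider severe-injury regression, in line with the existing coding.
- Keep items 10 to 17 out of that model's predictors. The current wording does not exclude them, and their blanks would remove the same riders again.
- Define severe and mild by item 12 category before the data are seen; without this the recode cannot give a complete outcome.
- Restrict the mild-versus-severe comparison and all summaries of items 10 to 17, including days to return to sport and work, to riders with at least one injury at item 9.
- Report how many riders left item 9 blank, and how many entered zero there but ticked item 12.

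**Cost.** One line on the form in five languages and a short recode rule in the SAP. If the forms are already printed, the recode still works wherever item 9 was answered.

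### Severity is collected on five ordered levels but tested as severe versus not severe at an unstated cut, which costs power and leaves the cut open to choice after the results are seen

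*Combined protocol and SAP*

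**What the plan says.** Section 3 (Statistical analysis plan) uses severity as a binary variable in two named analyses:

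- The logistic regressions, fitted "in elites and amateurs separately", have the dependent variable "no severe injury = 0 versus severe injury = 1".
- The chi-squared tests compare groups on injury prevalence and on "the occurrence of severe, respectively mild injury events".

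Results with a p-value below 0.05 "will be considered as statistically significant".

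Item 12 of the questionnaire asks for severity, with the instruction "if more than one injury occurred, choose the most severe one". It offers five answers in ascending order: no treatment needed, self-treatment, treatment by a doctor, treatment in the ER, and "Overnight hospitalization".

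Neither section 3 nor the questionnaire says which of these answers are severe or mild. Section 3 names no ordinal analysis and no analysis at alternative cuts. It also does not say whether riders who were never injured are coded 0 or left out, and item 12 has no answer for them.

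**The concern.** Five ordered levels allow four binary cuts. Two are plausible readings of severe: doctor treatment or above, and ER treatment or above. The plan does not choose between them, so its outcome cannot be rebuilt from the text.

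Two consequences follow for the comparison of elites with amateurs. A binary split ignores differences within each side of the cut, so it has less power than a test that uses all five levels, and the loss depends strongly on where the cut falls. And while the cut is open, it can be settled after the results are known, in which case the nominal 5% error rate no longer holds.

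The cut also sets the number of severe events available to the regression in elites.

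**Working it through.** **Inputs from the documents.** Five ordered levels (item 12); binary outcome and a 0.05 threshold (section 3). The survey "will be conducted on the participants of the Swiss Epic mountain bike event in 2017", but no sample size, expected distribution or effect size is given, so there is no figure of the plan's own to reproduce.

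**Assumed inputs.** All riders counted are injured. Amateur distribution over the five levels: 35/30/20/10/5%. Elites and amateurs: 30/120 or 50/200. Exact proportional odds with common odds ratio (OR) 1, 2 or 2.5. Two-sided 5% tests.

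**Step 1: share severe at each cut.** In amateurs, the shares at or above levels 2, 3, 4 and 5 are 0.65, 0.35, 0.15 and 0.05. In elites, the share is OR·c / (1 − c + OR·c). At OR 2:

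- doctor or above: 0.70 / (0.65 + 0.70) = 0.519, or about 26 of 50 elites;
- ER or above: 0.30 / (0.85 + 0.30) = 0.261, or about 13 of 50 elites.

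**Step 2: information kept by one cut.** Relative efficiency against the full scale is [1 − c³ − (1 − c)³] / [1 − Σp³]. Here Σp³ = 0.042875 + 0.027 + 0.008 + 0.001 + 0.000125 = 0.079, so the denominator is 0.921.

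- Level 2 or above, and doctor or above (c = 0.65 and 0.35): 0.6825 / 0.921 = 0.74
- ER or above (c = 0.15): 0.3825 / 0.921 = 0.42
- Overnight stay (c = 0.05): 0.1425 / 0.921 = 0.15

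**Step 3: power.** 40,000 simulated surveys per row; uncorrected chi-squared test at each cut, and Mann-Whitney with tie correction on all five levels.

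| Elites/amateurs, OR | Self-treated+ | Doctor+ | ER+ | Overnight | Ordinal | Gain over best cut |
|---|---|---|---|---|---|---|
| 30/120, 2 | 29.2% | 40.6% | 31.1% | 17.6% | 47.1% | 6.5 |
| 30/120, 2.5 | 45.3% | 61.4% | 50.2% | 28.1% | 70.2% | 8.8 |
| 50/200, 2 | 47.5% | 59.3% | 45.3% | 25.7% | 69.1% | 9.8 |
| 50/200, 2.5 | 68.3% | 82.3% | 69.5% | 41.3% | 89.6% | 7.3 |

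The gain over the worst cut runs from 47.1 − 17.6 = 29.5 points to 89.6 − 41.3 = 48.3 points.

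**Step 4: error rate when the cut is picked afterwards (OR 1).** The smaller p-value of the doctor+ and ER+ cuts is below 0.05 in 9.0% (30/120) and 8.4% (50/200) of surveys. The smallest of all four is below 0.05 in 15.2% and 15.1%. If the four tests were independent, the figure would be 1 − 0.95⁴ = 18.5%.

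**Step 5: other assumptions.** With equal groups of 100, OR 2 and four distributions from flat to very mild, ordinal power is 76% to 79%, against 62% to 68% at the best cut and 16% to 41% at the worst. With equal groups of 50 to 400 and no true difference, the error rate is about 8% to 9% for the better of the two middle cuts and 15% to 17% for the best of four.

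**The case against.** A binary outcome is legitimate and easy to interpret, and one sentence fixing the cut would remove the choice after the results. That stands: dichotomising is not in itself an error, and the case for the ordinal test is the information it recovers. Against a well-chosen cut that recovery is modest, and the simulation assumes exact proportional odds, the setting most favourable to the ordinal test.

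The stated aim is descriptive, which lowers the consequence. It does not remove it, since section 3 still tests at 0.05 and looks for predictors, and even a percentage of severe injuries needs a definition.

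Section 3 never names item 12 as the source of the severe/mild split. That link is an inference. If another item were meant, the definition would be more open still.

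A reader might also infer more than the documents support:

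- *The ordering is never used.* The planned relative frequencies could show all five levels, and the planned correlations may include item 12. Binary use is established only for the chi-squared tests and the regressions.
- *The false-positive rate is 15%.* That requires trying all four cuts, including one that calls self-treated injuries severe.
- *The main model is shown to be underpowered.* The plan names no main model, and the calculation concerns elites versus amateurs, not the regressions within each group.
- *The cut will be picked from the results.* The documents leave this possible; they do not say it is intended.

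**Conclusion.** The concern holds for the elite-versus-amateur comparison of severity. The plan tests a binary version of a presumed five-level item at a cut it does not state. Under the assumed inputs, power runs from about 18% to 82% depending on cut and scenario, against 47% to 90% for an ordinal test. The gain is about 6 to 10 points over the best cut and about 30 to 48 over the worst. A choice between the two plausible cuts after the results gives about 9% false positives; about 15% is the worst case.

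These sizes rest on assumed sample sizes, an assumed distribution and exact proportional odds. The missing definition and the absence of any planned ordinal test rest on the text alone. No power or error rate has been shown for the separate regressions; for those, only the dependence of the event count on the cut is established. This is a worthwhile, cheap improvement and not a fatal flaw.

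**What to change.** 1. Add a five-level comparison of elites and amateurs among injured riders (Mann-Whitney or proportional-odds regression) alongside the planned chi-squared test. State that it is conditional on having been injured, since that population may differ from the one behind the binary outcome.
2. Before analysis, name item 12 as the source, fix one cut with a reason, and apply it to both groups. State whether uninjured riders are coded 0 or excluded, and show results at the neighbouring cut.
3. Choose the cut with the expected severe events among elites in mind. Under the 50/200, odds ratio 2 assumptions, moving from doctor or above to ER or above halves them, from about 26 to 13, which limits how many predictors the elite model can carry.
4. Treat days to return to sport (item 15) as exploratory only. Item 12 asks for the most severe injury and item 10 for the most recent, while item 15 specifies neither.

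The cost is wording in section 3; no new data are needed. The downside is that the ordinal analysis relies on roughly proportional odds, and the fixed binary version guards against that.
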